**Table 3: Adjunctive Antiplatelet and Anticoagulant Medication Regimen†**

Visit	Warfarin*		Aspirin		Clopidogrel /P2Y12 Inhibitor	
	Watchman #	WaveCrest	Watchman #	WaveCrest	Watchman #	WaveCrest
Discharge	Yes	No	Yes Per Watchman DFU	Yes 75-100mg	No (unless subject was on P2Y12 inhibitor prior to randomization)	75mg 12-48 hours post-procedure, then daily a
45-Day	Cessation per Watchman DFU (if LAA is closed)	No	Yes Per Watchman DFU	Yes 75-100mg	75mg daily with warfarin discontinuation per DFU	75mg daily a

3 Month	No b	No	Yes Per Watchman DFU	Yes 75-100mg	75mg daily with warfarin discontinuation per DFU	No
6 Month	No b	No	Yes Per Watchman DFU	Yes 75-100mg	No	No
≥ 1 Year	No b	No	Yes Per Watchman DFU	Yes 75-100mg	No	No

# All Watchman adjunctive medication should be administered per the product DFU

† For subjects not implanted with a LAA occlusion device, antiplatelet and anticoagulant medications will be per physician discretion.

\* Alternative vitamin K antagonists (e.g., acenocoumarol or phenprocoumon) may be used according to geographic standard of care.

a Prasugrel 5-10 mg QD or ticagrelor 60-90 mg BID may be used in place of clopidogrel in subjects unable to take clopidogrel but may not be used with warfarin. Also, prasugrel is contraindicated in subjects with a history of prior stroke/TIA and both are contraindicated in subjects with a history of hemorrhagic stroke.

b If subject has remained on warfarin for non-closure, cessation of warfarin remains per Watchman DFU

**Table 4: Schedule of Assessments†**

Assessment	Screening/ Baseline	Treatment Visit (Implant Procedure)	Discharge	Office Visit				Phone Follow-up 3m, 1.5y, 2.5y, 3.5y, 4.5y
				45d	6m	1y	2y, 3y, 4y, 5y	
Medical history	X							
Physical exam	X	X	X	X	X	X	X	
Blood work	X							
CHADS 2 /CHA 2 DS 2 - VASc	X							
HAS-BLED score	X							
TEE a	X	X		X	X h	X		
TTE a			X					
QVSFS b	X			X	X	X	X	X i
QoL	X			X	X	X	X	
Neurology exam				X f				
Brain Imaging (MRI – if contraindicated CT)	X c			X d				
mRS/NIH Stroke Scale				X e				
Medication Review	X	X	X	X	X	X	X	X
AE Monitoring e				X				

† Schedule of assessments for subjects implanted with an LAA occlusion device; subjects not implanted with an LAA occlusion device will not have TEE at follow-up.

a Follow the **Echocardiography Protocol** from the ECL for all TEE/TTE exams; submit TEE/TTE images from baseline; implant; discharge; 45-day visit; 6-month visit (if applicable); 1-year visit, as well as any unscheduled TEEs/TEEs due to AEs to ECL.

b Trial personnel must administer the QVSFS. If subject has symptoms resulting in QVSFS score > 0 since their most recent follow-up, a board-certified study Neurologist blinded to subject's randomization assignment and implanted device, to the extent possible, must evaluate the subject or otherwise provide rationale for why an in-

person neurology visit and exam are unnecessary. If there is any concern for stroke, subject must be brought in for **Unscheduled Neurology Visit** within 14 days following QVSFS administration; if stroke is suspected, stroke scale must be administered, and brain imaging must be performed. If stroke is confirmed, and a TEE is performed, to ascertain the mechanism of stroke, follow the **Echocardiography Protocol**. Re-administer mRS 90 days (+/-15) days after stroke.

c Brain imaging to be performed at baseline if subject has history of stroke or TIA; if an imaging study following the prior neurologic event is available, repeat imaging is not required per Neurology’s discretion

d Brain imaging to be performed if stroke or TIA is suspected at any time during follow-up.

e Adverse event monitoring is initiated upon the subject signing the informed consent form.

f If subject had symptoms resulting in QVSFS score > 0 since their most recent follow-up at any visit or if stroke or TIA is suspected at any time during follow-up, a visit with a board-certified study Neurologist is required. The study Neurologist may waive this visit if it is based solely on QVSFS change with documented rationale.

g If stroke is suspected by the study Neurologist, administer NIHSS. Also administer mRS at the visit and 90 (+/-15) days after any confirmed stroke

h Per physician discretion if closure is not confirmed with 45-day TEE or if part of study site SOC.

i Not required for the 3-month assessment

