	
 
WaveCrest arm subjects discontinuing clopidogrel (or P2Y12 inhibitor) must remain on 75-100mg aspirin daily indefinitely.
 
 
6 months post-implant
 
 
Subjects with peri-device flow >5mm at 45 days will undergo a TEE at 6 months.
 
Watchman arm subjects discontinuing warfarin and clopidogrel (or P2Y12 inhibitor) should take daily aspirin per the Watchman DFU indefinitely.
 
																																																																		
Number of Trial Sites	Up to 100 sites will participate in the trial in North America, Europe, Australia, and Asia																																																																		
Sample Size	
 
Up to 1,550 subjects will be randomized in a 1:1 ratio between the WaveCrest and Watchman devices. The trial design offers at least 80% power to establish non-inferiority for the effectiveness and safety hypotheses across the range of possible event rates.
 
Sites will be allowed up to 5 roll-in cases (up to 2 per operator) prior to randomization for a total of up to 500 roll-in subjects.
 
Up to 2,050 total subjects will be enrolled
 
																																																																		
Enrollment Phase	The enrollment phase is expected to last between 2 and 3 years.																																																																		

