Follow-up Evaluations	
Office follow-up: at 45 days, 6 months, 1, 2, 3, 4 & 5 years  Phone follow-up: at 3 month & 1.5, 2.5, 3.5, and 4.5 years  Transesophageal echocardiograms (TEE):
 
 
45-day visit
 
6-month visit (if LAA closure is not established at 45-day visit)
 
1-year visit
 
 
Summary of Study Assessments
 
  
 Test	Screening /Baseline	Treatment	Discharge	Office F/U	Phone F/U	
   
 Med Hx	X					
 
 Phys Exam	X	X	X	X		
 
 Blood work	X					
 
 QVSFS	X			X	X	
 
 QoL	X			X		
 
 Neuro eval	X	X (with stroke symptoms or QVSFS>0)*	
 
 TEE	X	X		X*		
 
 TTE			X			
 
 AE eval	X	X*	X	X	X	
 
 Med review	X	X	X	X	X	
  
 
* - see additional details in Table 4 of the CIP below
	Test	Screening /Baseline	Treatment	Discharge	Office F/U	Phone F/U	Med Hx	X					Phys Exam	X	X	X	X		Blood work	X					QVSFS	X			X	X	QoL	X			X		Neuro eval	X	X (with stroke symptoms or QVSFS>0)*				TEE	X	X		X*		TTE			X			AE eval	X	X*	X	X	X	Med review	X	X	X	X	X
Test	Screening /Baseline	Treatment	Discharge	Office F/U	Phone F/U																																																														
Med Hx	X																																																																		
Phys Exam	X	X	X	X																																																															
Blood work	X																																																																		
QVSFS	X			X	X																																																														
QoL	X			X																																																															
Neuro eval	X	X (with stroke symptoms or QVSFS>0)*																																																																	
TEE	X	X		X*																																																															

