### 6.8 Follow-up 6 Month Office Visit

- Perform physical exam
- Administer QoL questionnaire (see **Quality of Life Questionnaire - SF-36**)
- Qualified trial personnel who are blinded to subject's randomization and implanted device administer the QVSFS (see **Appendix III: Questionnaire for Verifying Stroke-Free Status**); If the subject has experienced symptoms resulting in a QVSFS score  $> 0$  since their most recent follow-up, a board-certified study Neurologist blinded to subject's randomization and implanted device, to the extent possible, must evaluate the subject or otherwise provide rationale for why an in-person neurology visit and exam are unnecessary. This **Unscheduled Neurology Visit** must be completed within 14 days of the QVSFS administration or site's awareness of the onset of stroke symptoms. (See **Section 6.12** for details of Unscheduled Neurology Visit)
- For subjects in the Watchman arm, if the LAA was closed at 45 days, clopidogrel may be discontinued per the product DFU but aspirin should continue per the product DFU.
- If the LAA was not closed at 45 days and the subject remains on warfarin (Watchman arm) or DAPT (WaveCrest arm), a TEE should be repeated at this visit. Discontinuation of warfarin (Watchman arm) or P2Y12 inhibitor (WaveCrest arm) is at physician discretion but is recommended if peri-device color Doppler flow demonstrated by TEE is  $\leq 5$ mm.
- If an adequate seal is not demonstrated, warfarin (Watchman arm) or P2Y12 inhibitor (WaveCrest arm) may be continued at Investigator discretion until flow  $\leq 5$ mm is noted. Watchman subjects who continue warfarin for 6 months post-implant are not required to start clopidogrel but should remain on aspirin per the product DFU.
- Sites that routinely perform a 6-month TEE as their standard of care (SOC) may perform a TEE in all subjects at that site. This is not required for sites that do not perform a 6-month TEE as part of their SOC.
- Evidence of device thrombus is recommended to be treated with a 6-week course of warfarin (+/- aspirin) and repeat TEE.
- Record cardiac medications, including antiplatelet and anticoagulant medications
- Record adverse events, device malfunctions and protocol deviations as appropriate

	Title: The WAVECREST 2 Trial  Clinical Investigational Plan	Doc. #: CHX_IP014	Rev: H
---	--	-----------------------------	------------------

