**Descriptive Effectiveness Endpoints**

The following effectiveness endpoints will be descriptively summarized:

 	Title: The WAVECREST 2 Trial  Clinical Investigational Plan	Doc. #: CHX_IP014	Rev: H
--	--	-----------------------------	------------------

- Primary effectiveness event rate at 6 months, 3 years, 4 years and 5 years
- Composite of all stroke, systemic thromboembolism, or TIA at 45 days, 6 months, and at each annual follow-up period
- Landmark analysis of primary effectiveness endpoint from the 45-day visit to the time of each annual follow-up period
- Landmark analysis of the incidence of ischemic stroke from 6 months following device implantation and discontinuation of oral anticoagulant and dual antiplatelet therapy
- Composite of all-cause stroke at 45 days, 6 months, and at each annual follow-up period
- Incidence of thrombus on the surface of the device at 45 days, 1 year, and throughout all follow-up
- Strokes adjudicated as ischemic, hemorrhagic, or indeterminate at 45 days, 6 months, and at each annual follow-up period - see definition in **Appendix I: Acronyms and Definitions**
- Strokes adjudicated as major or minor at 45 days, 6 months, and at each annual follow-up period - see definition in **Appendix I: Acronyms and Definitions**
- Stroke adjudicated as cardioembolic in origin at 45 days, 6 months, and at each annual follow-up period - see definition in **Appendix I: Acronyms and Definitions**
- Freedom from oral anticoagulants after each protocol-required follow-up visit
- Number of devices used per subject
- Procedural success – see definition in **Appendix I: Acronyms and Definitions**
- Technical success – see definition in **Appendix I: Acronyms and Definitions**
- Device success – see definition in **Appendix I: Acronyms and Definitions**
- LAA closure rate at 45 days, 6 months, and 1 year as reported by the ECL– see definition in **Appendix I: Acronyms and Definitions**
- Procedure time, device duration, contrast usage, and fluoroscopy time

 	Title: The WAVECREST 2 Trial Clinical Investigational Plan	Doc. #: CHX_IP014	Rev: H
--	---	-----------------------------	------------------

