- **Number of devices used per subject**

The number of devices used (i.e., attempted) will be summarized. The number of devices used will be summarized by the proportion of subjects in whom 0, 1, 2 or >2 devices were attempted. [REDACTED]
[REDACTED]

- **Procedural success**

The procedural success rate will be calculated as the proportion of subjects who experience successful placement and release of the occluder in the LAA with LAA closure (defined as no color flow Doppler flow > 5mm) and discharge from the cardiac catheterization laboratory without procedure-related complications [REDACTED]
[REDACTED]
[REDACTED]

- **Technical Success**

The technical success rate will be calculated as the proportion of subjects who experience successful placement and release of the occluder in the LAA with LAA closure (defined as no color flow Doppler flow > 5mm) and discharge from the cardiac catheterization laboratory without the occurrence of a device-related adverse event.

- **Device success**

Device success will be calculated as the proportion of subjects who have the device deployed and implanted in the correct position.

[figure not shown]
[figure not shown]
- **LAA closure rate at 45 days, 6 months, and 1 year**

LAA closure will be assessed in subjects whose 45-day, 6-month and 1-year TEEs have been evaluated by the Echocardiography Core Lab for residual leak/gap measurement. As defined in the protocol, LAA closure is defined as no residual leak or if leak is present, residual gap \leq 5mm. [REDACTED]
[REDACTED]
[REDACTED]

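### The 6-month LAA closure rate rests on a TEE subset enriched for subjects not closed at 45 days, so a crude rate is biased downward by an amount the documents do not fix

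*Protocol*

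**What the plan says.** Protocol 15.6 lists as one descriptive item "LAA closure rate at 45 days, 6 months, and 1 year as reported by the ECL". SAP 8.7.2 gives the analysis set: "LAA closure will be assessed in subjects whose 45-day, 6-month and 1-year TEEs have been evaluated by the Echocardiography Core Lab". The closure definition (residual gap of 5 mm or less) follows, and then redacted lines. SAP 8.7 attaches 95% confidence intervals and descriptive p-values to the endpoints in this group and says they will not support labeling.

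Table 4 schedules the 45-day and 1-year TEEs for all implanted subjects. The 6-month TEE is conditional, and four places describe the condition differently:

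- Synopsis, Post-Procedure Care: subjects with flow above 5 mm "at 45 days will undergo a TEE at 6 months".
- Synopsis, Follow-up Evaluations: "if LAA closure is not established at 45-day visit", with no mention of standard-of-care sites.
- Section 6.8: if the LAA was not closed at 45 days and the subject is still on warfarin (Watchman) or DAPT (WaveCrest), "a TEE should be repeated at this visit". The section adds: "Sites that routinely perform a 6-month TEE as their standard of care (SOC) may perform a TEE in all subjects at that site".
- Table 4, footnote h: "Per physician discretion if closure is not confirmed with 45-day TEE or if part of study site SOC".

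**The concern.** Whether a subject is imaged at 6 months depends on the outcome being measured. A subject with a leak at 45 days is a candidate for the scan; a subject who was closed has one only at a site that images routinely. If the rate is the number closed divided by the number with a core-laboratory reading, subjects with a known leak are over-represented in the denominator.

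The 6-month figure would then stand between two rates from near-complete imaging, with its own interval and p-value. A reader could take the difference for a loss of seal at 6 months that recovers by 1 year, when it comes from who was scanned.

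**Working it through.** **No plan figure to reproduce.** The documents state no expected 6-month closure rate, no number of 6-month TEEs and no share of routinely imaging sites. The only closure figure for the device is 100% at a gap of 5 mm or less at 45 days (Protocol 2.7, device version 1.3, N=73). There is no Watchman figure.

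**Quantities, all assumed:**

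- c: proportion closed at 45 days
- s: proportion of closed subjects who have a 6-month TEE (routinely imaging sites)
- u: proportion of non-closed subjects who have one
- g: proportion of non-closed subjects who are closed by 6 months
- k: proportion of closed subjects who stay closed

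**Formulas**

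- Rate among those imaged = [(1−c)·u·g + c·s·k] / [(1−c)·u + c·s]
- Rate in all implanted subjects = (1−c)·g + c·k
- Non-closed share of those imaged = (1−c)·u / [(1−c)·u + c·s]

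**Direction.** The first rate is below the second whenever s < u and g < k. If the share of subjects at routinely imaging sites is the same for closed and non-closed subjects, and those sites image everyone, then u = s + (1−s)·v, where v is the proportion of non-closed subjects imaged elsewhere. So u is at least s, and the bias is downward or zero.

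**Worked case.** c=0.97, s=0.10, u=1, g=0.3, k=0.99:

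- Imaged: (0.03×0.3 + 0.97×0.10×0.99) / (0.03 + 0.097) = 0.10503/0.127 = 82.7%
- All implanted: 0.009 + 0.9603 = 96.9%
- Bias: −14.2 points

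**Bias in points** (k=0.99, u=1; first value g=0.3, second g=0.5):

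| c | s=0 | s=10% | s=30% | s=50% |
|---|---|---|---|---|
| 0.90 | −62 / −44 | −29 / −21 | −12 / −8 | −6 / −4 |
| 0.97 | −67 / −48 | −14 / −10 | −4 / −3 | −2 / −1 |
| 0.99 | −68 / −49 | −6 / −4 | −2 / −1 | −0.7 / −0.5 |

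At s=100% and u=1 the bias is zero. If only half of the non-closed subjects are imaged (u=0.5), the bias at c=0.97 and s=10% falls to −7 / −5.

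**Are those imaged mainly non-closed subjects?** The non-closed share is one half at s = u(1−c)/c. With u=1 this is 11.1% at c=0.90, 5.3% at 0.95, 3.1% at 0.97 and 1.0% at 0.99. At c=0.95 the share is 0.05/(0.05+0.095) = 34% for s=10%, and 0.05/(0.05+0.285) = 15% for s=30%.

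**Precision.** SAP 8.5 randomizes 1250 to 1550 subjects 1:1, so 625 to 775 per arm. If all were implanted and imaged at 45 days, the non-closed group would be about 19 to 23 per arm at c=0.97 and 6 to 8 at c=0.99. Without routine imaging the 6-month rate would rest on those subjects alone.

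**The case against.** The other side has five good arguments.

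- **Redaction.** The lines after the closure definition in SAP 8.7.2 are blacked out and could hold a denominator or missing-TEE rule. This stands: one can say only that the visible text shows no correction.
- **Ambiguous wording.** The SAP sentence could mean each visit's own TEE, or subjects with all three TEEs. This stands, but it does not remove the problem. On the second reading the same selection would reach the descriptive 45-day and 1-year rates too.
- **Size.** A reader might infer that the imaged subjects are mostly leakers by design and that the rate must be far too low. The documents do not support that. They allow routinely imaging sites to scan everyone, and with high 45-day closure a few percent of closed subjects scanned would outnumber the leakers. With closure near the 100% of the earlier study and some routine imaging, the bias is small.
- **Consequence.** The endpoint is descriptive. The tested closure endpoint is at 45 days with its own 45-day TEE denominator (Protocol 15.5, SAP 8.4) and is unaffected. The 1-year TEE is scheduled for all implanted subjects. All of this stands and keeps the point minor.
- **Remedy.** Carrying subjects closed at 45 days forward as closed assumes that no leak re-opens, which the documents do not show. This stands and limits how such a figure may be used.

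A reader might also infer a biased comparison between arms. Section 6.8 ties the scan to arm-specific medication, and the implanting investigator knows the arm (Protocol 4.2), so different selection is possible. Nothing in the documents shows that it will occur.

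**Conclusion.** The point holds as a minor one. On the visible text, a crude 6-month closure rate would come from a set enriched for 45-day non-closure. It would be biased downward and would not be comparable with rates from the visits at which everyone implanted is imaged. The direction needs only that closed subjects are imaged less often than non-closed ones and are more likely to be closed at 6 months.

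The size cannot be fixed from the documents. Under the assumed inputs it runs from 44 to 68 points if no closed subject is imaged, through 4 to 29 points if 10% are, to 0.5 to 0.7 points at 99% closure with half of closed subjects imaged. It disappears if all are imaged. A general statement that the rate will be far too low goes further than the documents allow. No primary or tested secondary result changes.

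Separately, the four protocol statements disagree on whether the 6-month TEE is required, advised or discretionary, and in whom.

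**What to change.** In SAP 8.7.2, replace the single crude 6-month rate with two, each by arm and with its denominator:

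- (a) closure at 6 months among subjects not closed at 45 days, showing how many of them were imaged;
- (b) closure at 6 months among all subjects at sites that image routinely at that visit, with those sites identified before the analysis.

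State whether the analysis set is each visit's own TEE or all three. If an all-implanted rate is wanted, give the rule for subjects without a 6-month TEE. If that rule carries 45-day closure forward, label the result a sensitivity analysis and check the assumption against the 1-year TEE in the same subjects.

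In the protocol, reconcile the two synopsis rows, section 6.8 and Table 4 footnote h on whether, and in whom, the 6-month TEE is done. Which of them should govern is for the sponsor and the investigators.

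The cost is a few sentences in each document, one table and, if site practice is not already recorded, a site-level flag. No added imaging or change in sample size is needed.

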### 6.13 Subject Trial Completion

Subjects will be considered to have completed participation in the trial when they have completed 5-year follow-up or have discontinued from the trial. The appropriate eCRF must be completed for the subject when:

- Subject has completed 5-year follow-up, or
- Subject has died before 5-year follow-up is complete, or
- Subject has requested to withdraw from the trial prior to 5-year follow-up with no further contact or review of charts

When the subject’s participation in the clinical trial has been completed the subject will return to the medical care as per physician’s recommendation.

	Title: The WAVECREST 2 Trial  Clinical Investigational Plan	Doc. #: CHX_IP014	Rev: H
---	--	-----------------------------	------------------

**6.14 Any Known or Foreseeable Factors that May Compromise the Outcome of the Clinical trial or the Interpretation of the Results**

All foreseeable factors that may compromise the outcome have been taken into account by clinical trial design and well-defined subject selection criteria.

**6.15 Criteria and Procedures for Subject Withdrawal or Discontinuation**

Every roll-in and randomized subject (including those who did not undergo a Treatment Visit or did not receive a device implant), shall remain in the trial until completion of 5-year follow-up; however, subject participation in any clinical trial is voluntary and the subject has the right to withdraw at any time without penalty or loss of benefit. Possible reasons for discontinuation may include but may not be limited to the following:

- Subject refuses to continue participation in the trial
- Subject is deceased (cause must be documented)
- Lost-to follow-up (defined below).

It is the Sponsor’s intent to apply the principles from FDA’s guidance on Data Retention When Subjects Withdraw From FDA-Regulated Clinical Trials to the WAVECREST 2 trial so as to minimize bias and ensure trial integrity. If a subject voluntarily withdraws from the trial, every effort must be made to obtain full information on any new or ongoing adverse events through the date of subject discontinuation.

Investigators must report subject withdrawals to their respective IRB/EC as defined by their institution’s procedure. If a subject withdrawal is related to the investigational device, the Investigator shall document the reason for subject discontinuation as related to investigational device and request subject’s permission to follow his/her status outside the clinical investigation.

Subjects who discontinue participation prematurely will be included in the analysis of results (as appropriate) but will not be replaced. At Sponsor’s request, the Investigator may consult public records, such as those establishing survival status, after subject withdrawal. Alternatively, the Sponsor may contract with a subject search organization for the Investigator in order to establish survival status of discontinued subjects.

